6.1 FORMULATION, PACKAGING AND LABELING

6.1.1 FORMULATION

The oral formulation of VOR is available as a 100-mg capsule.

6.1.2 PACKAGING & LABELING

VOR will be packaged by the ACH research pharmacy in an open-label fashion in high-density polyethylene bottles. Labeling will be labeled as per Health Canada requirements, which includes the drug name, pill count, dosing instructions and storage instructions.

6.1.3 STORAGE

The study medication must be stored in a secure place at room temperature (not above 25°C).

6.2 DOSE AND SCHEDULE OF STUDY MEDICATION

6.2.1 DOSAGE RATIONALE

Several studies have investigated the MTD, and DLT, when administered as a single agent and in combination of other cancer treatment in pediatric populations with various malignancies⁵⁰⁻⁵⁴. VOR administered orally to these populations at a dosage of 230 mg/m²/day was found to be efficacious, and was overall considered to be well-tolerated in these populations.

6.2.2 DOSAGE

Participants will take 100 mg VOR capsules orally to meet dose of 230 mg/m² once per day as closely as possible. The following dose rounding table will be used as a reference for drug dosing dispensed based on BSA, where

$$BSA(m^2) = \text{SQRT}([\text{height}(cm) \times \text{weight}(kg)]/3600)$$

| VOR dosage (mg/m ²) | BSA | | | | | | | |
|---------------------------------|------------|-------------|----------|-------------|------------|-------------|----------|-------------|
| | 0.5 – 0.74 | 0.75 – 0.99 | 1 – 1.24 | 1.25 – 1.49 | 1.5 – 1.74 | 1.75 – 1.99 | 2 – 2.24 | 2.25 – 2.49 |
| 230 | 100 | 200 | 200 | 300 | 300 | 400 | 400 | 500 |

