2.1 PRIMARY OBJECTIVES

Characterize the safety and tolerability of 230 mg/m²/day VOR, administered orally, in a pediatric population with medically intractable epilepsy in combination with standard of care anti-seizure drugs.

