3.1.1 DOSAGE

Participants will be administered 230 mg/m²/day of VOR in addition to standard of care anti-seizure medication for a duration of 6 weeks. The dosage was chosen based on the MTD of five Phase 1 trials, which included pediatric patients or were exclusively pediatric trials⁵⁰⁻⁵⁴.

Briefly, in a Phase 1 study, Fouladi et al⁵⁰, investigated VOR alone and in combination with 13cRA in children with recurrent or refractory malignancies (Part A – solid tumors; Part B – leukemia). Three dose levels were utilized: 180 mg/m² VOR; 180 mg/m² VOR + 13cRA; 230 mg/m² VOR; 300 mg/m² VOR). In the solid tumors group at a dose of 180 mg/m² VOR, one patient suffered an SAE, however this was deemed to not related to treatment. At the 230 mg/m²/d VOR dose level, there were no DLT in the first three patients enrolled. At 300 mg/m²/d DLT occurred in 2 of 6 patients but since the AEs were of different classes, the cohort was expanded to six additional evaluable patients. At this dose, 2 patients had DLT thereby exceeding the MTD, therefore three additional patients were subsequently enrolled at the 230 mg/m². In this cohort, only one experienced a DLT, defining 230 mg/m²/d as the MTD and recommended phase II dose for children with solid tumors. The recommended phase II dose was then trialed in the refractory leukemia group. Two of the first five patients experienced DLT, therefore this dose did not appear tolerable in children with refractory leukemia; no other dose finding was attempted in this population.

In a Phase 1 study, Hummel et al⁵¹ investigated VOR in combination with TEM in children with recurrent or refractory brain or spinal cord tumors. Three dose levels were tested: 230 mg/m² VOR + 150 mg/m² TEM; 300 mg/m² VOR + 150 mg/m² TEM; 300 mg/m² VOR + 200 mg/m² TEM. There were no DLTs at Dose level 1 or 2. At dose 3, 4 patients had DLTs, therefore the recommended phase 2 dose for the combination of VOR and TEM as 300 mg/m² VOR + 150 mg/m² TEM.

In a Phase 1 study, Muscal et al⁵² investigated VOR in combination with BOR in children with recurrent or refractory solid tumors, including CNS tumors. Three dose levels were tested: 180 mg/m² VOR + 1.3 mg/m²/d BOR; 230 mg/m² VOR + 1.3 mg/m²/d BOR; 300 mg/m² VOR + 1.3 mg/m²/d BOR. At the third dose level, 2 patients experienced DLTs, thus dose level 2 (230 mg/m² + 1.3 mg/m²/d BOR) is the recommended phase 2 dose.

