3.2 RATIONALE FOR STUDY DESIGN

The pre-clinical data for VOR is highly suggestive of a potential novel therapy for the treatment of medically intractable epilepsy. However, VOR is currently approved only for the treatment of cutaneous manifestations in patients with advanced CTCL who have progressive, persistent or recurrent disease subsequent to prior systemic therapies. A safety/efficacy trial of VOR in a population with medically intractable epilepsy is largely warranted, given the existing need for additional therapeutic strategies. The target population will consist of pediatric patients with medically intractable epilepsy, recruited from the Alberta Children's Hospital (ACH) Neurology Outpatient Clinic, with medically intractable epilepsy despite exhaustive treatment with current standard therapies, who would be anticipated to benefit from a novel intervention strategy.

The primary endpoints of this study are the safety & tolerability of VOR in pediatric patients with medically intractable epilepsy. The secondary endpoints of this study is the efficacy of VOR in reducing seizure frequency in this population pool. Participants will receive 230 mg/m²/day of VOR in addition to standard of care anti-seizure medication for a duration of 6 weeks, to evaluate the risk/benefit of VOR at this dosage on top of standard of care anti-seizure treatment.

The proposed study design will allow for the study objectives to be met within the context of a typical Canadian clinical epilepsy treatment centre. Completion of this pilot study in this population will begin to indicate the safety & efficacy profile of VOR at a dosage of 230 mg/m²/day as a potential therapy for the treatment of seizures, and based on findings may justify a larger randomized study to further investigate this potential avenue in children with medically intractable epilepsy in a rapidly translational manner.

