6.3 ASSESSMENT OF COMPLIANCE

Assessment Accountability and subject compliance will be assessed by maintaining adequate drug dispensing and return records. Participants will be asked to return all used and unused drug supply containers at each visit as a measure of compliance. An investigator may decide to withdraw a participant within the first 14 days, if the participant is found to be non-compliant. Compliance will be defined as having taking study medication as directed 80% of the time. Participants will be encouraged to discuss issues affecting compliance with the investigator.

A Drug Dispensing Log will be kept current with the following information:

- Identification of the participant to whom the study medication was dispensed
- Date[s], quantity of the study medication dispensed to the participant
- Date[s] and quantity of the study medication returned by the participant

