8.2.2 ANALYSIS

8.2.2.1. SAFETY & TOLERABILITY ANALYSIS

Safety and tolerability will be assessed by calculating the incidence rate of AEs per number of drug days from the time medication is started through to the completion of the SFU (or 42 days following the last dose of study medication). This will be done for the following time points: 14 days following drug initiation; 30 days following drug initiation; 42 days following drug initiation; and 42 days following drug discontinuation. AEs will be further stratified by mild/moderate AEs, severe AEs, and SAEs, as well as project specific AEs (thromboembolism, hyperglycemia, gastrointestinal disturbances, dehydration, hematologic disturbances, QT/QTc prolongation).

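### The dose table in section 6.2.2 is labelled 230 mg/m² but rounds to 200 mg/m²: at 43% of its BSA values one more capsule would be nearer 230, and at none would one fewer.

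*Combined protocol and SAP*

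**What the plan says.** Section 6.2.2 sets the dosing rule: "Participants will take 100 mg VOR capsules orally to meet dose of 230 mg/m² once per day as closely as possible". Section 6.1.1 gives the only unit available: "The oral formulation of VOR is available as a 100-mg capsule". BSA is the square root of height (cm) times weight (kg) over 3600. A rounding table, described as a reference for the dispensed dose, covers eight BSA bands of 0.25 m² from 0.5 to 2.49. Its dose row, with the label 230 first, reads "230 | 100 | 200 | 200 | 300 | 300 | 400 | 400 | 500".

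The rest of the protocol describes the dose under study as 230 mg/m²/day. The primary objective (section 2.1) is to "Characterize the safety and tolerability of 230 mg/m²/day VOR, administered orally, in a pediatric population with medically intractable epilepsy". Section 3.2 expects that the completed pilot "will begin to indicate the safety & efficacy profile of VOR at a dosage of 230 mg/m²/day" and says the findings may justify a larger randomized study. The safety analysis (section 8.2.2.1) works by "calculating the incidence rate of AEs per number of drug days from the time medication is started". Section 6.3 requires a log that includes "Date[s], quantity of the study medication dispensed to the participant", together with returns.

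**The concern.** A table that gives the whole-capsule dose nearest to 230 × BSA should miss the target in both directions about equally. This one steps up at BSA 0.75, 1.25, 1.75 and 2.25, which are the midpoints for a 200 mg/m² target, not a 230 one. If the pharmacy follows it, the average dose is well below the dose named in the objectives.

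The dose level is what this trial studies. Section 3.1.1 treats 180, 230 and 300 mg/m² as separate levels with different toxicity decisions. If tolerability or lack of effect is credited to 230 when the average was nearer 200, a later trial that delivers a true 230 would expose children to more drug than the pilot tested. The planned analysis would not reveal this, because it counts drug days and reports no mg/m² received.

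**Working it through.** **Inputs.** Target 230 mg/m² once daily, and the bands and doses of the table (6.2.2); capsule 100 mg (6.1.1). Assumption: each BSA from 0.50 to 2.49 in steps of 0.01 counts equally, giving 200 values, 25 per band.

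**Formulas.** Delivered dose = tabulated mg ÷ BSA. Nearest whole-capsule dose for target T = 100 × floor(T × BSA ÷ 100 + 0.5).

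**Spot checks at T = 230.**
- BSA 1.24: target 230 × 1.24 = 285 mg. The table gives 200 (161 mg/m²); 300 is nearer (242 mg/m²).
- BSA 1.74: target 400 mg. The table gives 300 (172 mg/m²); 400 gives 230 mg/m².
- BSA 2.00 to 2.24: target 460 to 515 mg. The table gives 400 throughout, so it is never nearest.

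**Full grid at T = 230.**

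| BSA band | Table dose (mg) | Mean delivered (mg/m²) | Values where one more capsule is nearer |
|---|---|---|---|
| 0.50–0.74 | 100 | 163.5 | 9 of 25 |
| 0.75–0.99 | 200 | 231.5 | 0 |
| 1.00–1.24 | 200 | 179.3 | 16 |
| 1.25–1.49 | 300 | 219.6 | 0 |
| 1.50–1.74 | 300 | 185.6 | 22 |
| 1.75–1.99 | 400 | 214.2 | 4 |
| 2.00–2.24 | 400 | 188.9 | 25 |
| 2.25–2.49 | 500 | 211.2 | 10 |

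The total is 86 of 200 (43%). One capsule fewer is nearer at 0 of 200.

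**Which target the table fits.** At T = 200 it agrees with nearest rounding at all 200 values (exact ties at 0.75, 1.25, 1.75 and 2.25 rounded up). In steps of 0.1, only T = 200.0 to 200.8 reproduces it.

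**Size of the shortfall.**

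| | Table | Nearest rounding to 230 |
|---|---|---|
| Mean (mg/m²) | 199 | 228 |
| Mean as share of 230 | 87% | 99% |
| Range (mg/m²) | 135–267 | 154–303 |
| Mean absolute distance from 230 | 33 | 21 |
| Share of values above 230 | 9% | 48% |

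At the 86 misrounded values the table averages 182 mg/m².

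**Dependence on the BSA range.**

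| BSA range | Misrounded | Table mean (mg/m²) |
|---|---|---|
| 0.50–1.49 | 25 of 100 (25%) | 199 |
| 0.50–1.74 | 47 of 125 (38%) | 196 |
| 0.50–1.99 | 51 of 150 (34%) | 199 |
| 0.60–1.80 | 47 of 121 (39%) | 198 |
| 0.60–2.00 | 52 of 141 (37%) | 200 |
| 0.70–2.00 | 48 of 131 (37%) | 203 |

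In every range all the errors are on the low side.

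**The case against.** **The 43% is a share of table values, not of children.** This stands. The two bands from BSA 2.00 upward supply 35 of the 86 misrounded values, and few participants aged 2 to 17 may be that large. With 12 participants, the number affected is unknown. A cohort mostly in 0.75–0.99 would average 231 mg/m² with none misrounded; one mostly in 1.00–1.24 would average 179. The mean over broad ranges, 196 to 203, barely moves.

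**The capsule size forces wide spread.** It does, and no table could deliver exactly 230 at most BSA values. But spread does not explain a one-sided bias: the same capsule, rounded to the nearest, averages 228.

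**Low rounding is protective.** In the first pediatric trial summarised in section 3.1.1, 230 was the MTD for solid tumors, and of the 300 mg/m² level the section says "At this dose, 2 patients had DLT thereby exceeding the MTD". At the 86 misrounded values the extra capsule would average 250 mg/m² and reach 303. So the error creates no overdose hazard, and that is a good reason not to raise doses automatically. It does not make the label right. No section says the low rounding is intended, and the table is not a cap at 230, because it exceeds 230 at 18 of 200 values (267 at BSA 0.75).

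**The table is only a reference.** True, but no rule for departing from it is given.

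**The delivered dose can be recovered afterwards.** Yes, from height, weight and the dispensing log. The plan does not say this will be done.

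**Conclusion.** The point holds. The table contradicts the rounding instruction in its own section, and always downward. On equal weighting of the table's BSA values, 43% are misrounded (25 to 39% on the narrower ranges above) and the mean delivered dose is 199 mg/m², about 13% below the stated 230. The shortfall among the actual participants depends on their BSA and on the pharmacy using the table as printed. The contradiction, its direction and the exact match to 200 mg/m² do not depend on the weighting. This should be fixed because the dose is named in the objectives and in the conclusion the pilot is meant to support.

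**What to change.** 1. Decide which dose is meant.
   - *If the low rounding is intended:* keep the table, replace the rounding instruction with the rule actually used (nearest 100 mg to 200 mg/m²), relabel the row, and state the dose as about 200 mg/m²/day, range 135 to 267.
   - *If 230 mg/m² is intended:* the dose changes at BSA (100k + 50) ÷ 230 for k = 1 to 5, that is between 0.65 and 0.66, 1.08 and 1.09, 1.52 and 1.53, 1.95 and 1.96, and 2.39 and 2.40 m². The maximum then rises to about 303 mg/m² (200 mg at BSA 0.66), and 48% of BSA values lie above 230 instead of 9%. The sponsor should take this as a safety decision.
2. In either case, derive each participant's delivered mg/m²/day from height, weight and the dispensing and return log. Report the median and range, and list adverse events and seizure response against it. With 12 participants this is descriptive only.
3. Word the objectives and conclusions for the dose delivered.
4. State whether and when the pharmacy may depart from the table.

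The cost is low: one sentence in 6.2.2, the dose wording in the objectives, and one derived variable. No new data are collected.

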6.2.3 DOSE INTERRUPTIONS

If a dose is missed, it should be taken as soon as possible. If the participant does not remember until it is nearly time for the next dose, the participant should skip the missed dose and go back to the regular schedule. A double dose of should not be taken.

There will be no temporary interruptions of study medication due to safety reasons. If study medication is stopped due to safety reason, there will be no re-challenge.

6.3 ASSESSMENT OF COMPLIANCE

Assessment Accountability and subject compliance will be assessed by maintaining adequate drug dispensing and return records. Participants will be asked to return all used and unused drug supply containers at each visit as a measure of compliance. An investigator may decide to withdraw a participant within the first 14 days, if the participant is found to be non-compliant. Compliance will be defined as having taking study medication as directed 80% of the time. Participants will be encouraged to discuss issues affecting compliance with the investigator.

A Drug Dispensing Log will be kept current with the following information:

- Identification of the participant to whom the study medication was dispensed
- Date[s], quantity of the study medication dispensed to the participant
- Date[s] and quantity of the study medication returned by the participant

6.4 DESTRUCTION OF STUDY MEDICATION

Following reconciliation against the documentation of quantity dispensed and returned, destruction of drug will be done as per the ACH Research pharmacy's standard operating procedures.

This includes:

- Identity [batch numbers or subject numbers] of study medication destroyed
- Quantity of study medication destroyed
- Date of destruction
- Method of destruction
- Name and signature of responsible person looking after study medication destruction

SECTION 7: SAFETY INSTRUCTION AND GUIDANCE

7.1 ADVERSE EVENTS AND LABORATORY ABNORMALITIES

7.1.1 CLINICAL ADVERSE EVENTS

An AE is any untoward medical occurrence in a patient or clinical investigation participant, administered a pharmaceutical product, which does not necessarily have a causal relationship with the treatment. An AE can therefore be any unfavorable and unintended sign including an abnormal laboratory finding, symptom, or disease temporally associated with the use of a medicinal investigational product, whether or not considered related to the medicinal investigational product. Pre-existing conditions which worsen during a study are also to be reported as AEs.

7.1.1.1 INTENSITY

All clinical AEs encountered during the clinical study will be reported in the study record. The intensity of AEs will be graded by the investigator on a three-point scale (mild, moderate, severe) and reported in detail on the CRF.

| | |
|----------|---|
| Mild | discomfort noticed but no disruption of normal daily activity |
| Moderate | discomfort sufficient to reduce or affect daily activity |
| Severe | inability to work or perform normal daily activity |

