The second metric reviewed was SAEs. The incidence of SAEs as reported for the adult VOR studies was 7%; 5% for the pediatric VOR studies, 0.8-10% for VPA studies, and 4.7-8.2% for AEDs. Given the differences in study designs and populations, the rates of SAEs are comparable. The most common SAEs reported in the adult VOR studies were thromboembolic events and anemia; in the pediatric VOR studies, SAEs consisted of thromboembolic events, bleeding/hemorrhage, neuropathy, and hypoxic/acute respiratory distress. Indeed the product monograph indicates that thromboembolic events maybe associated with VOR therapy with an overall incidence rate of 6.8%. However in the pediatric VOR studies, all SAEs were not considered to be related to VOR. Typically however, severity of events in cancer trials are graded using the National Institutes of Health CTCAE Grading system, whereas clinical trials typically utilize the International Council for Harmonisation of Technical Requirements for Pharmaceuticals for Human Use (ICH)/ Good Clinical Practice Guidelines (GCP) for rating severity of events. Utilizing the ICH-GCP definitions, a "serious" AE includes events that are life-threatening. Events rated as Grade 4 using the CTCAE system are considered to be life-threatening. Given this, Grade 4 events using the CTCAE reporting could be considered to be "SAEs". An analysis could not be carried out on the adult VOR studies because Grade 3 and 4 events were grouped together for reporting, however in the pediatric VOR studies, inclusion of the Grade 4 as SAEs caused the incidence rate of SAEs to jump to 65%, with again the most commonly reported events comprising hematologic events and nausea. Although this is an important consideration, it is also important to note that the term 'life-threatening' in the ICH/GCP definition of an SAE refers to an event in which the patient was at risk of death at the time of the event; it does not refer to an event which hypothetically might have caused death if it were more severe. It is not absolutely clear whether these Grade 4 events meet the ICH/GCP criteria for a serious event. However, the fact remains that Grade 4 hematologic events, which according to the CTCAE are platelets $< 25 \times 10^9/\text{L}$; absolute neutrophil count $< 0.5 \times 10^9/\text{L}$; and lymphocyte count $< 0.2 \times 10^9/\text{L}$; are medically quite serious, regardless of whether they meet a pre-set definition. As discussed in the above section, it is unlikely that the rates of incidence found in the Phase 1 VOR pediatric studies are expected in an overall medically stable population; it is anticipated that incidence of SAEs in the proposed population will be that typically seen with VPA/AEDs. However potentially serious hematologic events cannot be ruled out and hematologic testing, in addition to other lab safety testing will be conducted every 2 weeks to monitor study patients. Patients will also be advised of signs of symptoms associated with these hematologic events and to contact the study team in the event of these signs and symptoms. Regarding the other events cautioned to require special monitoring in

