7.1.1.3 SERIOUS ADVERSE EVENTS

An SAE is any experience that suggests a significant hazard, contraindication, side effect or precaution. It is any AE that at any dose fulfills at least one of the seriousness criteria following criteria:

- is fatal/results in death (**NOTE:** death is an outcome, not an event)
- is life-threatening (i.e. refers to an event in which the patient was at immediate risk of death at the time of the event; it does not refer to an event which could hypothetically have caused a death had it been more severe).
- requires in-patient hospitalization or prolongation of existing hospitalization;
- results in persistent or significant disability/incapacity;
- is a congenital anomaly/birth defect;
- is medically significant or requires intervention to prevent one or other of the outcomes listed above.

SAE reporting procedures are described in [Section 7.2](#). Death is the outcome of an event and will not be reported as the SAE term, rather the event causing the death will be reported as the SAE. The only exception is when the cause of death is not known; these cases will be reported as “Death Unknown”.

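### The intensity scale has no criterion for symptom-free laboratory or ECG abnormalities, so hematologic, glucose and QTc events are counted but not ranked by severity

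*Combined protocol and SAP*

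**What the plan says.** - **Scale.** Section 7.1.1.1: "The intensity of AEs will be graded by the investigator on a three-point scale (mild, moderate, severe"). Mild is "discomfort noticed but no disruption of normal daily activity", severe is "inability to work or perform normal daily activity", and moderate lies between them on the same two ideas. There is no laboratory or ECG threshold.
- **What enters the data.** Sections 5.3.1 and 7.1.1 count abnormal laboratory findings as adverse events. Section 7.1.2 records an out-of-range result if it comes with symptoms, changes study medication, or changes concomitant therapy. A result can therefore be recorded without any symptom.
- **Analysis.** Section 8.2.2.1: "AEs will be further stratified by mild/moderate AEs, severe AEs, and SAEs, as well as project specific AEs". The project-specific list includes hyperglycemia and ends with "dehydration, hematologic disturbances, QT/QTc prolongation". No grading, shift table or worst-value table is planned for laboratory or QTc values.
- **Seriousness.** Section 7.1.1.3 gives alternative criteria, any one of which is enough. The life-threatening criterion is narrow ("it does not refer to an event which could hypothetically have caused a death had it been more severe"). A separate criterion covers medically significant events.
- **Background.** Section 1.1.3 describes pediatric toxicity in CTCAE grades. Section 1.1.4.3 gives Grade 4 limits for platelets, neutrophils and lymphocytes and says that such events "are medically quite serious, regardless of whether they meet a pre-set definition". It closes by anticipating a higher proportion of hematologic events than with other anti-epileptic drugs.

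**The concern.** The toxicity that the protocol singles out is measured by a number, but the scale that grades it contains no numbers. A fall in platelets or neutrophils often causes no discomfort until a complication occurs, and a long QTc may be found only on the tracing. When such a finding becomes a recorded event, the investigator has no written basis for assigning it a level.

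At stake is the description of severity in a 12-child pilot whose results may justify a larger randomized study (section 3.2). A slight count fall that prompts a change in a concomitant drug and a platelet count below 25 x 10^9/L that ends treatment would look the same in the hematologic row. The severe row could be almost empty while Grade 3-4 cytopenias were present. The results also could not be set beside the Grade 3-4 figures in section 1.1.3.

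**Working it through.** **1. Follow one event through the plan.** Take a child whose platelets fall below 25 x 10^9/L without bleeding or symptoms, and whose study drug is stopped for it.

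- Section 7.1.2: recorded, because study medication changed.
- Section 7.1.1.1: not mild as worded, because no discomfort is noticed; not moderate or severe, because activity is unaffected. Mild is the nearest level.
- Section 7.1.1.3: serious only if judged life-threatening, medically significant, or meeting another listed criterion. No threshold is given.
- Section 8.2.2.1: counted under hematologic disturbances, possibly under SAEs, but not under severe AEs on the scale's wording.

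Section 7.1.1.1 refers to clinical AEs, so it could be read as leaving laboratory findings out. On that reading the event has no grade at all, and section 8.2.2.1 would stratify it by a value that does not exist. Neither reading leads to severe.

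**2. What kind of event is affected (Table 1, n = 110).** First, the protocol's own figures:

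- Grade 3-4 thrombocytopenia: (16 + 16)/110 = 32/110 = 29.1%, as stated.
- Grade 4 column: 72, as stated. Grade 3 column: 146, against 145 in the text, a difference of one that does not matter here.
- Grade 3-4 total: 146 + 72 = 218.

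| Rows | Grade 3 | Grade 4 | Grade 3-4 | Share of 218 |
|---|---|---|---|---|
| Leukopenia | 23 | 9 | 32 | |
| Lymphopenia | 19 | 19 | 38 | |
| Thrombocytopenia | 16 | 16 | 32 | |
| Neutropenia | 10 | 2 | 12 | |
| Anemia | 13 | 1 | 14 | |
| Hemoglobin | 1 | 1 | 2 | |
| ANC | 1 | 0 | 1 | |
| **Blood-count rows** | **83** | **48** | **131** | **60%** |
| Chemistry and QTc rows | 17 | 5 | 22 | 10% |
| **Both** | **100** | **53** | **153** | **70%** |

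At Grade 4 alone, blood counts are 48/72 = 67% (the text says 66%).

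**3. Illustration for 12 participants.** The protocol has no power calculation, so there is no planned figure to reproduce. Assume a Grade 3-4 thrombocytopenia rate p. The expected number of cases is 12p, and P(at least one) = 1 - (1 - p)^12.

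- p = 5.8% (adult studies): 12 x 0.058 = 0.70 cases; 1 - 0.942^12 = 51%.
- p = 29.1% (pediatric oncology studies): 12 x 0.291 = 3.49 cases; 1 - 0.709^12 = 98%.

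The documents give no symptom-free share. Over its full range of 0 to 100%, the expected number with no route to the severe row runs from 0 to 0.70 in the first case and from 0 to 3.49 in the second, provided the events are recorded at all.

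**The case against.** The strongest reply is that the plan has other ways to show these events.

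- **Separate rows.** A reader might infer that the plan cannot show hematologic or QTc toxicity at all. It can: the sentence that sets the severity split also tabulates these classes on their own. What is lost is severity within them.
- **SAE route.** A reader might infer that a silent Grade 4 count cannot be an SAE because there is no immediate risk of death. That is only one of several criteria. Section 7.1.1.3 admits medically significant events, section 5.3.1 important medical events, and section 7.1.2 reports qualifying laboratory results as SAEs. This stands, but the route is discretionary. Section 1.1.4.3 itself is unsure that Grade 4 counts meet the serious-event definition, and seriousness is not severity. Grade 3 falls may never enter.
- **Tabulated as mild.** This too is an inference. Mild requires noticed discomfort, so the grade is undefined rather than fixed at mild.
- **Reach.** Intensity is not part of the primary endpoint in section 8.1.1 or of the benchmarks in section 5.2.1, which use overall AEs, SAEs, deaths and discontinuations. It is a further stratification.
- **Comparability.** The protocol says the oncology findings cannot be extrapolated to epilepsy (section 1.1.4), so losing the comparison with section 1.1.3 has limited weight.
- **QTc.** One event in 110 was reported and low incidence is expected (section 1.1.4.3). QTc shares the grading gap but is not among the toxicities expected most.

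These points narrow the concern. None supplies a criterion for grading a symptom-free abnormality.

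**Conclusion.** The concern holds in a limited form. For hematologic disturbances, hyperglycemia and QT/QTc prolongation, the planned split between mild/moderate and severe does not measure severity. These events are counted, and some may be called serious, but their depth is not ranked. A low severe-AE rate could therefore coexist with Grade 3-4 cytopenias.

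The 60% (131 of 218) describes the type of event that the scale does not address. It comes from heavily pre-treated oncology patients, mostly on combination therapy, and counts events by type, not by whether they were symptom-free. It is not an expected rate or an effect size for this trial, and the illustration for 12 children carries the same limit.

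A reader might also infer that children disabled by epilepsy before dosing have no room to worsen on a functional scale. The documents do not describe baseline function, so this cannot be claimed.

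Whether section 7.1.2 leaves silent abnormalities unrecorded is a separate matter; recording more of them would still leave them without a meaningful grade.

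**What to change.** - **Section 7.1.1.1:** keep the three-point scale for symptomatic events. Grade laboratory and ECG events by the numeric criteria of the CTCAE linked in section 1.1.3, and name the version, since the link's path contains both 4.03 and 4.0. The protocol prints numeric limits only for Grade 4 platelets, neutrophils and lymphocytes, so the remaining limits must be brought in from that document.
- **Section 8.2.2.1:** place laboratory and ECG events of CTCAE Grade 3 or higher in the severe stratum, and tabulate the worst grade per participant for the hematologic, glucose and QTc classes.

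The cost is protocol and CRF wording. Blood results are already scheduled at weeks 2, 4, 6 and 12. The ECG is scheduled three times (screening, Visit 3 and safety follow-up), so the QTc table will rest on few tracings. No treatment rule changes. The drawbacks are two grading systems on the CRF and a severe-AE rate that may look less favourable.
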